4.0 Enrollment/Randomization

We will conduct a single center, randomized, double-blind, double-dummy, parallel design trial comparing oral metolazone, intravenous chlorothiazide, and oral tolvaptan in combination with loop diuretics in patients hospitalized for hypervolemic acute heart failure. The duration of the study will be 48 hours from the first dose of the study thiazide or tolvaptan medication. Vanderbilt University Medical center will be the study site. IRB approval will be obtained from the Vanderbilt University Medical Center IRB.

All patients will provide informed consent prior to enrollment. After enrollment, all patients will be randomized in a 1:1:1 fashion at VUMC using a random number table in the investigational drug services pharmacy. The investigational pharmacists will perform randomization, and investigators will be blinded to the treatment arm.

5.0 Study Procedures

5.1 Background and Standard of Care Therapies

All patients will be started on a 2L/day fluid restriction and a 2g/day sodium restriction. Decisions regarding the initiation, titration, or discontinuation of standard heart failure medications (ACEI, ARB, Aldosterone Antagonists, Beta Blockers, digoxin, hydralazine, nitrates) are left to the discretion of the treating physicians. All electrolyte repletion, loop diuretic dose titration, and concomitant therapies to enhance diuresis if needed will be utilized at the provider's discretion.

To prevent confounding heterogeneity in the diuretic treatment approach, a stepped care algorithm similar to the CARRESS-HF¹⁹ trial will be utilized for loop diuretics, both initial doses and subsequent dose changes, and for concomitant inotropes and vasodilators. The stepped care algorithm and the initial diuretic treatment regimen are delineated in Study Flow Diagram below. A minimum furosemide equivalent dose of 580mg/24hrs (100mg IV bolus + 20mg/hr infusion rate) must be ordered at enrollment.

[figure not shown]
[figure not shown]
[figure not shown]
[figure not shown]
5.2 Randomization

All patients will be randomized in a 1:1:1 fashion at VUMC using an electronic randomization tool embedded in REDCAP. Patients will be randomized to either:

- 1) intravenous chlorothiazide 500mg IV Q12H + an oral placebo capsule Q12H
- 2) intravenous placebo infusion Q12H + a capsule containing oral metolazone 5mg PO Q12H
- 3) intravenous placebo infusion Q12H + a capsule containing oral tolvaptan 30mg once daily and placebo capsule in the evening dose.

(Relative potency^{21, 22}: Metolazone 100 fold more potent than chlorothiazide)

Hypervolemic AHF with <2L UOP in past 12 hours on \geq Furosemide 240mg/day

5.3 Blinding

This study will be double blinded. Blinding will be performed by the enrolling site's investigational drug service pharmacy. A double-dummy strategy will prevent investigators from knowing the treatment arm during observation.

5.4 Study Outcomes

The primary outcome will be 48-hour standing scale weight change (kg) from enrollment among the metolazone, intravenous chlorothiazide, and tolvaptan arms, using metolazone group as the comparator group for all other groups.

Secondary outcomes, using metolazone as the comparator group for each, will be:

- 48 hour net urine output (mls)
- mean change in serum creatinine, blood urea nitrogen, and eGFR at 24 hours, 48hours, and at hospital discharge
- mean change in diuretic efficiency at 24 and 48 hours from baseline value at enrollment
- mean change in serum potassium at 24 and 48 hours from baseline value at enrollment
- mean change in serum sodium at 24 hours, 48hrs, and at discharge from baseline value at enrollment
- cumulative dose of potassium (mEq) and magnesium (g) supplementation administered at 24 and 48 hours
- incidence of severe hypokalemia
- need for escalation in study-directed loop diuretic therapy at 24 and 48 hours
- addition of vasoactive or inotropic medication at 24 and 48 hours
- Treatment failure (definition below)
- Patient-scored congestion visual analog scale score at baseline, 24 and 48 hours (Appendix B)
- new cardiac arrhythmias (atrial and ventricular) during the study period
- receipt of inotropic therapy, dopamine, or nitroglycerin; requirement of ultrafiltration or hemodialysis during index hospitalization
- in-hospital mortality
- pharmacoeconomic analysis of the direct costs in each arm including the cost of:
 - study medication
 - additional non-trial protocol laboratory analysis cost related to monitoring of electrolytes
 - treatment of study medication related adverse effects (arrhythmias, hypotension, electrolyte repletion)
 - escalation of loop diuretic therapy doses
 - addition of additional therapies for suboptimal diuresis (inotropic therapy, vasodilators)
 - new initiation of renal replacement therapies (hemodialysis or ultrafiltration)
- Spot urinary electrolytes and diuretic urine concentration
- Pharmacokinetics and pharmacodynamics of the diuretics in the urine and blood
- Fractional excretion of sodium

5.5 Study Definitions

- Urine output: Total urine volume (ml) from time of study enrollment to 48 hours
- Hypokalemia: Serum potassium value < 3.5mEq/L
- Severe Hypokalemia: Serum potassium value < 3.0mEq/L
- Hyponatremia: Serum sodium value < 135mEq/L

- Severe Hyponatremia: Serum sodium value < 130mEq/L and a decrease of 5mEq/L or more from enrollment serum sodium
- Overcorrection of serum sodium: increase in serum sodium from baseline by ≥ 12 mEq/L in 24 hours, increase in >8 mEq/L in 12 hours, or receipt of intravenous fluids because of symptoms of overcorrection of serum sodium regardless of the numerical rise
- Hypomagnesiemia: Serum magnesium value < 2mEq/L
- Diuretic efficiency = 24hr urine output/ 24hr Lasix equivalents in milligrams
- Weight: Standing weight on the same scale as used for baseline weight measurement
- New Atrial Arrhythmia: A “new” diagnosis of atrial arrhythmia (includes atrial fibrillation, atrial flutter, ectopic atrial tachycardia) lasting > 30 seconds OR any atrial arrhythmia which causes hemodynamic instability (MAP < 60 and requiring intervention)
- New Ventricular Arrhythmia: Ventricular tachycardia lasting longer than 30 seconds, or frequent non-sustained VT causing hemodynamic instability with MAP < 60 mmHg requiring intervention or > 1 intra-cardiac defibrillation or external cardiac defibrillation shock or ventricular fibrillation requiring defibrillation
- Hypotension: SBP < 85 for 2 repeated measurements within 30 minutes or lasting at least 30 minutes or symptomatic hypotension necessitating clinical intervention (defined as vasopressor support, intravenous fluid boluses, or initiation of inotropes)
- Treatment failure: Patients requiring additional non-study diuretic (spironolactone doses >75 mg/day, eplerenone > 75 mg/day, non-study thiazides (at a dose of metolazone 2.5mg or greater equivalence) or loop diuretics, or systemic acetazolamide (for diuretic indication), triamterene, or amiloride therapy) at any time during the 48-hour randomization period. These patients will be considered treatment failures for the purpose of analysis of the primary endpoint and all secondary endpoints.
- Patients whose cardiologist adds inotropic or vasodilator medications will not be considered treatment failures. Patients who require an increase in the loop diuretic regimen will also not be considered treatment failures.
- Medication costs will be defined as the Redbook average wholesale price at the time of the trial to reduce inter-institutional price differences and improve external validity of the analysis.

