3.0 Inclusion/Exclusion Criteria

Inclusion Criteria

Criteria for inclusion will be:

- Age of 18 years or older
- Hospital admission for hypervolemic decompensated heart failure complicated by loop diuretic resistance.
 - Hypervolemia will be diagnosed by the admitting provider as either (i) pulmonary artery catheterization with a pulmonary capillary wedge pressure greater than 19mmHg plus a systemic physical exam finding of hypervolemia (peripheral edema, ascites, or pulmonary edema on auscultation) or (ii) in the absence of pulmonary artery catheterization data 2 of the following signs or symptoms: peripheral edema ascites, jugular venous pressure > 10mmHg, or pulmonary edema on chest x-ray.
 - Loop diuretic resistance is defined as a provider decision to pursue combination diuretic therapy because of failure to reach provider defined adequate diuresis (can not exceed urine output of 2 L in past 12 hours) despite receipt of an intravenous loop diuretic dose of a furosemide equivalent of at least 240mg/day over at least the past 12 hours (40mg furosemide = 20mg torsemide = 1mg bumetanide).
- Standard-of-care monitoring, including 24 hour telemetry monitoring on an inpatient ward and a basic metabolic panel laboratory assessment twice daily during the study period.

Exclusion Criteria

Candidates will be excluded if they meet any of the following criteria at the time of enrollment:

- Decision to pursue hemodialysis by a nephrologist
- estimated glomerular filtration rate by the MDRD equation < 15ml/min/m²
- systolic blood pressure < 85mmHg
- pregnancy* or breastfeeding
- serum potassium < 3.0mEq/L
- serum sodium > 145mEq/L or < 130mEq/L
- severe malnutrition
- advanced liver disease
- inability to perform standing weights
- inability to collect and measure urine with either a foley catheter or urine collection containers
- concomitant therapy with strong CYP3A4 inhibitors/inducers (systemic ketoconazole, clarithromycin, itraconazole, telithromycin, saquinavir, nelfinavir, ritonavir, neofodone, rifampin, rifabutin, rifapentin, phenytoin, phenobarbital, carbamazepine, St. John's Wort), p-glycoprotein inhibitors (cyclosporine, erythromycin, tacrolimus, dronedarone, quinidine, or verapamil)
- non-study diuretics (spironolactone doses >75mg/day, eplerenone > 75mg/day, non-study thiazides or loop diuretics, or systemic acetazolamide, triamterene, or amiloride therapy)
- Thiazide medication administered in the previous 24 hours prior to randomization

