5.7 Research Blood, Plasma, and Urine Collection

We will collect 20 ml of blood (10ml of serum and 10ml of plasma) at baseline (after consent), at 24 hours, and at 48 hours/study conclusion. We will serially collect urine produced during the study period for analysis. Analyses will include fractional excretion of sodium, diuretic pharmacokinetics/dynamics, and measures of hemoconcentration.

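### Change in diuretic efficiency subtracts a baseline that eligibility does not assure and that may be taken at a lower loop dose; adjusting for baseline would serve the comparison better

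*Combined protocol and SAP*

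**What the plan says.** - **Definition (section 5.5).** "Diuretic efficiency = 24hr urine output/ 24hr Lasix equivalents in milligrams".
- **Outcome (section 5.4).** One of the secondary outcomes is "mean change in diuretic efficiency at 24 and 48 hours from baseline value at enrollment", with metolazone as comparator.
- **Analysis (section 9.3).** Continuous secondary outcomes are compared with metolazone by Student's t test, two-sided at 0.05. No covariate is named. Section 9.1 gives 60 patients in three equal groups, so 20 per arm.
- **Before enrollment (section 3.0).** Loop resistance is judged "despite receipt of an intravenous loop diuretic dose of a furosemide equivalent of at least 240mg/day over at least the past 12 hours". The urine criterion uses the same length of time: "can not exceed urine output of 2 L in past 12 hours".
- **After enrollment (section 5.1).** "A minimum furosemide equivalent dose of 580mg/24hrs" must be ordered, whatever the arm.
- **Urine data.** Section 5.5 counts urine output from enrollment onward ("Urine output: Total urine volume (ml) from time of study enrollment to 48 hours"), and section 5.7 says "We will serially collect urine produced during the study period for analysis". Section 5.6 lists urine collection on Day 1, and Appendix A lists it at screening and baseline, but neither gives a look-back period.

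No section states which hours of urine and dose make up the baseline efficiency value, or where the pre-enrollment figures come from.

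**The concern.** A change score needs a baseline that exists for every patient and measures the same thing as the follow-up value. Neither is assured here. The definition calls for 24 hours of urine and dose, while the entry criteria secure 12. The baseline is also a ratio whose denominator the protocol itself raises at enrollment for anyone who entered on less than 580 mg/day.

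Two things are at stake. First, patients who enter at different prior doses get different shifts in their change score that have nothing to do with the study drug. That spread is noise in a comparison of 20 against 20. Second, the mean change within an arm, which is how section 5.4 words the outcome, mixes response with the dose step. Efficiency per milligram of loop diuretic bears directly on a trial about diuretic resistance, so the measure deserves an analysis that uses it well.

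**Working it through.** **1. The plan's own figures.** The minimum order reproduces: 100 mg + 20 mg/h × 24 h = 580 mg. The power statement in section 9.2 also reproduces (20 per arm, 1.5 kg, SD 1.6 kg, two-sided 0.05): 82.4% by the t test, against 82.3% stated. It concerns weight; the plan gives no mean, SD or power for diuretic efficiency.

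**2. Baseline window.** The definition needs 24 h; eligibility secures 12 h. Take a patient with only 12 h of loop therapy at 240 mg/day (120 mg given) and, as an assumption, 1,500 ml of urine in each 12 h.
- Literal 24-hour ratio: 3,000 / 120 = 25 ml/mg.
- Matched 12-hour ratio: 1,500 / 120 = 12.5 ml/mg.

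The plan does not choose between such constructions.

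**3. Dose step.** With urine output held constant, efficiency changes only through the denominator.

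| Prior dose, mg/day | Step to 580 mg | At 3,000 ml/24 h, before → after (ml/mg) |
|---|---|---|
| 240 | 580/240 = 2.42-fold | 12.5 → 5.2 (a 59% fall) |
| 480 | 580/480 = 1.21-fold | 6.25 → 5.17 |
| 580 | none | 5.17 → 5.17 |

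**4. Does it bias the comparison?** A two-arm simulation was run with 20 per arm and 4,000 runs per scenario. Its inputs are assumptions: baseline urine 2,500 ml/24 h (SD 800, capped at 4,000), on-study urine 4,500 ml/24 h (SD 1,500), correlation 0.5, and an on-study dose equal to the larger of 580 mg and the prior dose.
- With no arm effect, the mean between-arm difference in change lay between −0.014 and 0.021 ml/mg, and the change-score t test rejected in 4.3% to 5.9% of runs. There is no bias and no material inflation of type I error.
- The reference arm's own mean change was −2.6 ml/mg with all patients at 240 mg/day, +1.3 with prior doses spread over 240–580, and +3.5 with all at 580. The on-study urine distribution was the same throughout, so the prior dose alone set the sign.
- With an arm effect of 1,500 ml/24 h, power of the change score against on-treatment efficiency alone was 76% v 86% (all at 240), 78% v 87% (240–580), 80% v 84% (240–800) and 95% v 87% (all at 580).

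**5. Change score against covariate adjustment.** Assume on-treatment SD 2, arm difference 1.8 ml/mg and 20 per arm. With baseline SD *s* and correlation *r*:
- variance of change = *s*² + 4 − 4*rs*
- residual variance with baseline as covariate = 4(1 − *r*²)
- first minus second = (*s* − 2*r*)², which is never negative.

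| *s* | *r* | SD of change | Power, change | Adjusted SD | Power, covariate |
|---|---|---|---|---|---|
| 4 | 0.3 | 3.90 | 30% | 1.91 | 83% |
| 3 | 0.3 | 3.07 | 44% | 1.91 | 83% |
| 3 | 0.5 | 2.65 | 55% | 1.73 | 89% |
| 2 | 0.5 | 2.00 | 79% | 1.73 | 89% |
| 1.5 | 0.5 | 1.80 | 87% | 1.73 | 89% |
| 3 | 0.8 | 1.84 | 85% | 1.20 | >99% |
| 1.5 | 0.8 | 1.20 | >99% | 1.20 | >99% |

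On-treatment values alone give 79%. Over *s* from 1.5 to 4 and *r* from 0.3 to 0.8, adjusted power was never below change-score power, even after giving up one degree of freedom.

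**The case against.** The strongest reply is that the planned test compares arms, not time points. The dose minimum is common to all arms and allocation is random, so the step cancels in expectation; the simulation agrees. A reader might infer that the outcome mostly reflects the protocol's dose step. For the comparison with metolazone the documents do not support that; it concerns only the change within an arm.

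A reader might also infer that each arm will show a spurious loss of efficiency. That is not established even in sign. The 59% fall needs a patient at the eligibility floor whose urine does not rise after a higher loop dose and a second diuretic. The distribution of prior doses is not given.

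Nor can the outcome be called partly uncomputable as a matter of fact. Twelve hours is a minimum, these are inpatients whose urine must be measurable, and many may have 24 hours of records. The share who do not cannot be derived. Dividing 12-hour urine by a 24-hour dose, which would halve the baseline, is described nowhere in the plan.

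On power, 44% to 55% for the change score is one corner of assumed inputs. Other plausible inputs give 79% to 95%, and the change score beats unadjusted on-treatment values when every patient enters at 580 mg/day.

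All of this stands. What remains is the unassured baseline, the noise from prior dose, and an adjusted analysis that did at least as well in every case checked. Preferring adjustment is a general principle, but it has particular force where the protocol changes the baseline's denominator by a different factor for different patients.

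**Conclusion.** The point holds as a minor one. The plan subtracts a baseline whose 24-hour window is not secured by the entry criteria. For any patient entering below 580 mg/day, that baseline is measured at a lower loop dose, with a denominator step between 1 and 2.42-fold on a daily-rate basis. The comparison with metolazone remains valid. Its precision suffers to an extent the documents cannot settle, because they give no SD, correlation or effect size for this measure; the power ranges above are illustrative. The within-arm mean change should not be interpreted as response to the study drug. One secondary outcome is affected.

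**What to change.** Reword sections 5.4, 5.5 and 9.3.

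- **Outcome.** On-treatment diuretic efficiency over hours 0–24 and over hours 24–48, with urine and loop dose taken from the same hours. Stating the second window matters because the minimum order delivers 580 mg in the first 24 hours but 20 × 24 = 480 mg in the next if the infusion rate is unchanged.
- **Baseline.** Urine volume divided by loop dose over the same 12 pre-dose hours already assessed for eligibility, in ml/mg, with the data source named.
- **Analysis.** Each arm against metolazone by a linear model for on-treatment efficiency with baseline efficiency as covariate, in place of an unadjusted t test on change.
- **Reporting.** Within-arm change may still be shown descriptively, with a note that the loop dose may have changed at enrollment.

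The cost is wording, one degree of freedom, and a baseline resting on 12 rather than 24 hours and so somewhat noisier. No new visit or measurement is needed, since the 12-hour urine output and loop dose are already checked at entry.

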5.6 Study Outcome Timeline

Day 1: Baseline standing weight, BMP every 12 hours, urine collection, 20ml blood collection dyspnea score.

Day 2: 24 hour urine collection/quantification, BMP every 12 hours, 24 hour standing weight, 20ml blood collection, 24 hour dyspnea score, receipt of non-study diuretics, need of new inotropes or vasodilators

Day 3: 48 urine collection/quantification, 48 hour standing weight, 20ml blood collection, 48 hour dyspnea score, receipt of non-study diuretics, need of new inotropes or vasodilators.

End of study.

Day 30 (+/- 2 days): Telephone contact for the following events in past 30 days:

- ER visits and reason for visits
- Hospitalizations and reason for hospitalizations
- Serious adverse events

5.7 Research Blood, Plasma, and Urine Collection

We will collect 20 ml of blood (10ml of serum and 10ml of plasma) at baseline (after consent), at 24 hours, and at 48 hours/study conclusion. We will serially collect urine produced during the study period for analysis. Analyses will include fractional excretion of sodium, diuretic pharmacokinetics/dynamics, and measures of hemoconcentration.

6.0 Risks

This study will evaluate the addition of an oral thiazide, intravenous thiazide, or tolvaptan to augment intravenous loop diuretic therapy in patients with hypervolemic decompensated heart failure and diuretic resistance to adequately dosed loop diuretic monotherapy. Augmentation of loop diuretic therapy with a second diuretic (commonly a thiazide) is considered the standard-of-care in diuretic resistance and is endorsed by the AHA/ACCF and HFSA guidelines.^{8,9}

Tolvaptan

Several large scale clinical trials have demonstrated the safety of tolvaptan in patients with hypervolemic decompensated heart failure, including in those without hyponatremia. The EVEREST study evaluated 4,133 patients with decompensated heart failure randomized to placebo or tolvaptan for 60 days. The in-hospital serious adverse event rate was similar between tolvaptan (6.5%) and placebo (5.5%). The most common adverse effects of tolvaptan in these trials have been thirst (16%), dry mouth (8.4%), and polyuria. Hypernatremia occurred in 1.7% of tolvaptan patients vs 0.5% of placebo patients. Acute kidney injury, hypotension, and potassium derangements are not associated with tolvaptan therapy. As our duration of study is only 48 hours, it is not anticipated that study participation will be associated with increased risks beyond standard diuresis augmentation with a thiazide.

Hypernatremia/Over-correction of Serum Sodium

While hyponatremia is not the target population of this study, patients with a serum sodium range of 130-145mEq/L are eligible to participate. Relative to the thiazide arm, patients with hyponatremia randomized to tolvaptan are at the unique, albeit rare, risk of over-correction of serum sodium. Overcorrection of sodium is commonly defined as an increase in serum sodium by more than 12mEq/L in 24 hours. Overcorrection of serum sodium is most likely to occur when the serum sodium is < 125mEq/L at baseline, which is an exclusion criterion of our study. The SALT studies included patients with hyponatremia (serum sodium < 135mEq/L) from various disease states, including heart failure. Only 5 patients (2.2%) of patients experienced a rise if serum sodium > 12mEq/L during any 24 hour time period, on a dose of 15mg to 60mg a day of tolvaptan. No patients experiencing this rapid correction and no patients in EVEREST developed osmotic demyelination syndrome (ODS). The FDA package insert for tolvaptan records that cases of ODS have occurred in post-marketing surveillance. In our study, we will only randomize 20 patients to tolvaptan, calculating to 1-2 patients with hyponatremia being randomized to tolvaptan. The low rate of overcorrection in literature, small sample size, exclusion criteria (sodium < 130mEq/L, advanced liver disease, severe malnutrition), short duration of therapy in our trial, and twice daily serum sodium monitoring makes the risk of a patient experiencing overcorrection of serum sodium low in our study. All patients will be hospitalized for the duration of the study and will be monitored for neurologic symptoms.

To minimize this risk, patients who are at highest risk of ODS at enrollment (serum sodium < 130mEq/L) will receive a serum sodium assessment 12 hours after the first dose of study diuretic. If the serum sodium increases > 8mEq/L from baseline at 12 hours, they will receive protocolized management to prevent ODS.

- 1) Intravenous D5W at 3ml/kg/hr
- 2) Repeat serum sodium every 2 hours
- 3) Neurologic monitoring for symptoms such as speech disturbances, altered mental status, and seizure activity
- 4) D5W and every 2 hour serum sodium labs will be continued until the serum sodium is < 8mEq/L above baseline sodium

Patients will continue the loop diuretic therapy during this protocol. If the patient does not develop symptoms of ODS and responds to intravenous D5W therapy by hour 18 (6 hours after first serum sodium), they will be eligible for the scheduled second study diuretic dose at 24 hours. Patients experiencing any neurologic symptoms or who do not respond to intravenous D5W

therapy by hour 18 (6 hours after first serum sodium) will not be eligible for repeat study medication administration. All patients will be followed per the study protocol through Day 30.

Hepatic toxicity

Hepatotoxicity occurred in 3 patients in the TEMPO study, which evaluated the effects of Tolvaptan 60-120mg daily in a polycystic kidney disease patient population. In all 3 patients, the hepatic toxicity occurred after 3 months of therapy and resolved with tolvaptan discontinuation. Our study protocol will exclude patients with advanced liver disease, consistent with the updated FDA package labeling recommendations, and will administer a lower dose for only 48 hours.

Thiazides (Metolazone or Chlorothiazide)

In accordance with previous trials evaluating combination thiazide and loop diuretics (DOSE, CARRESS-HF), the metabolic risks include gout, hypokalemia, and hyponatremia. The risks include: hyponatremia, hypokalemia, gout flare/attack, and cardiac arrhythmias. In the CARRESS-HF study, ultrafiltration was compared to a step-wise diuretic protocol in 188 patients with hypervolemic, decompensated heart failure and worsening renal function. Of the 94 patients in the diuretic arm, 46% of participants received metolazone therapy. Only 3 (3%) patients experienced an electrolyte disorder, which included hypokalemia, hyponatremia, and hyperuricemia. Arrhythmic events were not specifically reported. A retrospective comparison of intravenous and oral thiazide diuretics found the rate of hypokalemia, defined as a serum potassium < 4mEq/L, to be 71% in the oral thiazide group and 83% in the intravenous thiazide group.¹⁴ Given the small size of previous combination diuretic studies, incidence rates of gout attacks and cardiac arrhythmias have not been quantified and are not provided in package labeling.¹¹ Our study will minimize hypokalemia and hyponatremia by monitoring the serum potassium and sodium every 12 hours during the study period. Electrolyte replacement will be performed at the discretion of the attending cardiologist, in accordance with standard of care practice.

7.0 Reporting of Adverse Events or Unanticipated Problems involving Risk to Participants or Others

A **Serious Adverse Event (SAE)** is an adverse event that:

- Results in death
- Is life-threatening
- Requires prolongation of hospitalization which is not specifically required by the protocol nor is it elective
- Results in permanent impairment of a body function or permanent damage to a body structure
- Requires medical or surgical intervention to preclude permanent impairment of a body function or permanent damage to a body structure

Additionally, important medical events that may not result in death, be life-threatening, or prolong hospitalization may be considered SAEs when they jeopardize the patient or require medical or surgical intervention to prevent one of the serious outcomes listed above. Example of such medical events include: allergic bronchospasm requiring intensive treatment in an emergency room or at home, blood dyscrasias or convulsions that do not result in prolonged hospitalization, or the development of drug dependency or drug abuse. Medical and scientific judgment must be exercised when classifying events as serious.

The determination of adverse event severity rests on medical judgment of a medically qualified investigator. The severity of SAEs will be graded using the following definitions:

- **Mild:** awareness of sign, symptom, or event, but easily tolerated;
- **Moderate:** discomfort enough to cause interference with usual activity and may warrant intervention;
- **Severe:** incapacitating with inability to do usual activities or significantly affects clinical status, and warrants intervention.

